9.1.1 Subject Disposition

A subject disposition summary will show number of subjects screened, number and percentage of screened subjects randomized (Part I) or enrolled (Part II), number and percentage of randomized (Part I) or enrolled (Part II) subjects who discontinued the study, and reasons for discontinuation with number of discontinued subjects as the denominator. Number and percentage of randomized (Part I) or enrolled (Part II) subjects in each analysis population will also be summarized.

Listings of subject disposition and subjects included in each analysis population will be provided. A listing showing that each randomized (Part I) and enrolled (Part II) subject met all inclusion/exclusion criteria will be provided. Reasons for screen failure will also be listed and summarized.

9.1.2 **Protocol Deviations**

Protocol deviations and PK sampling time deviations will be provided in separate listings. Protocol deviation listings will include the deviation description, category, and important/not important designation.

9.1.3 Demographic and Other Baseline characteristics

Demographic and other baseline characteristics will be summarized separately for the Safety population, PK populations (if different from Safety population), and screen failures.

9.1.4 Substance Use Habits

Alcohol, nicotine and xanthine/caffeine habits will be presented in listings.

9.1.5 Medical History

Any medical history findings will be presented in listings.

9.1.6 **Prior Medications**

Prior medications will be presented in listings and will include WHO-DD preferred name, WHO-DD drug class [anatomic therapeutic chemical (ATC) level 2], start and end date/time, dose, route, frequency, and indication. The listing will also include references to related AEs and medical history events, if applicable.

9.1.7 Childbearing Potential

Childbearing potential will be presented in a listing (Part I only).

9.1.8 Standard High Fat Breakfast

Standard high fat breakfast will be presented in a listing (Part II only).

9.1.9 Adverse event

For Part I of the study, a TEAE is defined as an AE with start date/time at or after IMP dosing.

For Part II of the study (a cross-over design):

A Period 1 (Fasted) TEAE is defined as an AE with start date/time at or after IMP dosing in Period 1 and no later than IMP dosing in Period 2.

A Period 2 (Fed) TEAE is defined as an AE with start date/time at or after IMP dosing in Period 2 and within the period of time equal to the interval from Period 1 dosing to Period 2 dosing.

The number and percentage of subjects reporting TEAEs and number of TEAEs will be presented both overall and by MedDRA SOC and PT, each in descending order of frequency (then alphabetically in case of ties). Separate summaries will be done for IMP-related TEAEs, treatment-emergent SAEs (TESAEs), and IMP-related TESAEs. TEAEs will also be summarized by maximum severity and by maximum toxicity grade within SOC and PT (refer to APPENDIX 3 – Tables for Laboratory Abnormalities for events with toxicity grades determined by the protocol); i.e., if more than one TEAE is coded to the same PT for the same subject, the subject will be counted only once for that PT using the most severe event for the summary by maximum severity, and using the most toxic event for the summary by maximum toxicity.

An overall summary table of TEAEs will be provided that shows incidence and number of events for each of the following:

- Any TEAE
- IMP-related TEAE
- TESAE
- IMP-related TESAE
- Severe TEAE
- TEAE with grade 3 or higher toxicity
- TEAE with outcome of study discontinuation
- Fatal TEAE

If any component of an AE starts date/time is missing such that it cannot be determined whether or not the AE was treatment-emergent, it will be counted in summaries as treatment-emergent. In summaries by relationship to IMP and severity, missing relationship will be summarized as "related" and missing severity will be summarized as "severe."

Protocol No. INDV-2000-101

Separate listings will be presented for TEAEs, TESAEs, TEAEs with outcome of study discontinuation, fatal TEAEs, and non-TEAEs.

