#### Table 2 Part 1 Single Ascending Dose IMP Dosing

Cohort		6	7	8	9
	Active	INDV-2000,	INDV-2000,	INDV-2000,	INDV-2000,
	N=6	Dose 6	Dose 7	Dose 8	Dose 9
Dose	Placebo	Placebo, to	Placebo, to	Placebo, to	Placebo, to
	N=2	match	match	match	match
Dosage Form (Active; Placebo)					

Safety and PK evaluation at each dose level. Sentinel dosing at all dose levels.

Part II of the study is a cross-over, food interaction evaluation where INDV-2000 will be given once under fasting conditions and once at completion of a standard FDA High-Fat Breakfast.

There will be 2 treatment arms of 8 subjects each, fed and fasted, with the same treatment order randomly assigned within subject. The same INDV-2000 dose will be used for fed and fasted conditions. Dose level is to be determined following Part 1.

For the fasting condition of Part II, subjects will receive INDV-2000 following an overnight fast of at least 10 hrs. Subjects will be administered INDV-2000 with 240 mL (8 ounces) of water.

No food will be allowed for at least 4 hours post-dose administration. Water is allowed as desired except for at least 1 hour before and at least 1 hour after drug administration.

For the food effect evaluation of Part II, subjects will consume a high-fat meal within 30 minutes prior to INDV-2000 administration. The high-fat meal should provide approximately 800 to 1000 calories, and should derive approximately 150, 250 and 500 to 600 calories from protein, carbohydrate and fat, respectively. Examples of an appropriate high-fat meal are provided in Secition 22.5, Appendix 5. Subjects should consume the entire meal in 30 minutes or less; however, the dose must be administered 30 minutes after the start of the meal. If the subject cannot complete the meal, the approximate percentage of the meal consumed should be recorded in the eCRF and continue with the study. Additionally, the start and finish time of the meal will be recorded in the eCRF. INDV-2000 will be administered with 240 mL (8 ounces) of water. No food will be allowed for at least 4 hours post-dose administration. Water is allowed as desired except for at least 1 hour before and at least 1 hour after drug administration.

Lunch will be provided at least 4 hr post- INDV-2000 (or - placebo) dose for both parts.

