## 14.4 Key End Point Analyses

#### 14.4.1 Primary Endpoint

The primary endpoint for the study is the incidence, seriousness, severity, and relationship to IMP of TEAEs in the Safety Population.

For Part I of the study, a TEAE is defined as an AE with start date/time at or after IMP dosing. For Part II of the study (a cross-over design), a Period 1 (Fasted) TEAE is defined as an AE with start date/time at or after IMP dosing in Period 1 and no later than IMP dosing in Period 2, and a Period 2 (Fed) TEAE is defined as an AE with start date/time at or after IMP dosing in Period 2 and within the period of time equal to the interval from Period 1 dosing to Period 2 dosing.

The number and percentage of subjects reporting TEAEs will be presented overall, by MedDRA system organ class (SOC) and preferred term (PT), each in descending order of frequency (then alphabetically in case of ties).

IMP-related TEAEs, treatment-emergent SAEs (TESAEs), IMP-related TESAEs, TEAEs leading to death, TEAEs leading to IMP discontinuation, and TEAEs leading to IMP interruption will be presented both overall and by SOC and PT. TEAEs will also be summarized by intensity within SOC and PT. In addition, TEAEs leading to death and IMP-related TEAEs leading to death will be summarized separately by PT.

In summaries by severity and relationship to IMP, if more than one TEAE is coded to the same PT for the same subject, the subject will be counted only once for that PT using the most severe and most related occurrence. Missing severity will be summarized as "severe" and missing relatedness will be summarized as "related."

Separate listings will be presented for TEAEs, TESAEs, TEAEs leading to IMP discontinuation and TEAEs leading to death.

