3.2 Treatments

The following treatment will be administered.

Part I: IMP will be administered under fasting condition. Subject will fast for at least 10 hrs prior to receiving the IMP. Subjects should be advised to avoid food and liquids other than water for at least 2 hours prior to dosing until at least 1 hour after dosing. Dose per cohort is detailed in Table 2.

Cohort		1	2	3	4	5
Dose	Active	INDV-2000,	INDV-2000,	INDV-2000,	INDV-2000,	INDV-2000,
	N=6	1 mg	5 mg	20 mg	50 mg	120 mg
Dose	Placebo	INDV-2000	INDV-2000	INDV-2000	INDV-2000	INDV-2000
	N=2	Placebo, 1 mg	Placebo, 5 mg	Placebo, 20 mg	Placebo, 50 mg	Placebo, 120mg
Dosage Form (Active; Placebo)						

Cohort		6	7	8	9
	Active	INDV-2000,	INDV-2000,	INDV-2000,	INDV-2000,
	N=6	Dose 6	Dose 7	Dose 8	Dose 9
Dose	Placebo	Placebo, to	Placebo, to	Placebo, to	Placebo, to
	N=2	match	match	match	match
Dosage Form (Active; Placebo)					

Part II: IMP will be administered under fasting conditions in Period 1 and at completion of a standard FDA high-fat breakfast in Period 2. The same INDV-2000 dose will be used for fed and fasted conditions. Dose level is to be determined following Part I.

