6.6 Standard High Fat Breakfast

Standard high fat breakfast applies only to Part II, Period 2 of the study. Subjects should consume the entire meal in 30 minutes or less, however, the dose must be administered no later than 30 minutes after the start of the meal. Data collected will include meal type, date, time, percent of meal consumed and comment if meal not provided.

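### The Part II Fasted and Fed TEAE windows overlap at the Period 2 dose, and adverse events that begin during the Period 2 breakfast are tabulated as Fasted

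*SAP*

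**What the plan says.** The two documents give the same rule for Part II. SAP 9.1.9 takes as a Period 1 (Fasted) TEAE an adverse event with "start date/time at or after IMP dosing in Period 1 and no later than IMP dosing in Period 2", and Protocol 14.4.1 agrees: "AE with start date/time at or after IMP dosing in Period 1 and no later than IMP dosing in Period 2". For the Fed condition, the SAP asks for a "start date/time at or after IMP dosing in Period 2 and within the period of time equal to the interval from Period 1 dosing"; the interval meant is the time between the two doses.

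The order of conditions is fixed in SAP 3.2: "IMP will be administered under fasting conditions in Period 1 and at completion of a standard FDA high-fat breakfast in Period 2". SAP 6.6 limits the meal to the second period: "Standard high fat breakfast applies only to Part II, Period 2 of the study".

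The meal comes before the dose. Protocol 9.3 states that "subjects will consume a high-fat meal within 30 minutes prior to INDV-2000 administration", and SAP 6.6 states that "the dose must be administered no later than 30 minutes after the start of the meal". Protocol 9.3 also provides that "the start and finish time of the meal will be recorded in the eCRF".

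Adverse events are collected continuously from consent (Protocol 10.1.1). SAP 9.1 presents the Part II safety summaries by period. TEAE incidence is part of the primary endpoint (Protocol 14.4.1; SAP Table 1).

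**The concern.** The Fasted window includes its end point and the Fed window includes its start point, and both points are the Period 2 dose. An onset recorded at that time therefore counts in both periods.

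The breakfast is what makes Period 2 the fed condition, yet the interval from meal start to dose lies wholly inside the Fasted window. A complaint that begins while the subject is eating would be reported under Fasted, at least a week after the fasted dose.

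The SAP treats the same minutes differently elsewhere. Under SAP 9.2, the last evaluation before the Period 2 dose is the Period 2 baseline, and SAP 9.1 defines study day within period. A pre-dose measurement that morning can thus be the Period 2 baseline, while an adverse event starting at the same moment is a Period 1 outcome.

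At stake is the accuracy of the Fasted column for the primary endpoint. With 8 subjects, a single event is visible in that column.

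**Working it through.** The plan attaches no figure to this point, and the sample size does not rest on a power calculation (Protocol 14.2; SAP 3.1.1). The check is to apply the windows as written.

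**Inputs**
- Part II sample size: 8 (SAP 3.1).
- Minimum interval between doses: 7 days, or 5 half-lives if longer (Protocol 4.3). I take 7 days = 168 h as the base case and show 10 and 14 days as well.
- Meal start to dose: up to 30 minutes = 0.5 h (Protocol 9.3; SAP 6.6).

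**Windows.** Let t be hours from the Period 1 dose and D the time of the Period 2 dose, here 168.
- Fasted: 0 ≤ t ≤ D.
- Fed: D ≤ t ≤ 2D.
- Meal: from t = 167.5 to t = 168.

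**Classification**

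| Onset t (h) | As written | With the fix |
|---|---|---|
| 100 | Fasted | Fasted |
| 167.5 | Fasted | Period 2 pre-dose |
| 167.75 | Fasted | Period 2 pre-dose |
| 167.99 | Fasted | Period 2 pre-dose |
| 168 | Fasted and Fed | Fed |
| 168.01 | Fed | Fed |

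**Size**
- Time affected: 8 × 0.5 h = 4 subject-hours.
- Meal share of the Fasted window: 0.5/168 = 0.30% for 7 days; 0.5/240 = 0.21% for 10 days; 0.5/336 = 0.15% for 14 days.
- Weight of one subject: 1/8 = 12.5 percentage points. This is a maximum, because a subject already counted for that term in the Fasted window adds nothing to its incidence.

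The documents give no adverse event rate for the meal interval, so an expected number of affected events cannot be calculated.

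**The case against.** The strongest reply is that the rule is a consistent dose-based convention. Until the Period 2 dose, the only study drug the subject has received is the fasted dose. Assigning an event to the most recent dose is therefore coherent, and Fasted then describes that dose rather than what the subject was eating at onset. This stands. It is why the events should not be moved into the Fed column, and why, after a dose has been given in a first-in-human study, they should stay treatment-emergent.

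A reader might infer that the rule takes events away from Fed and so distorts a fed-versus-fasted tolerability comparison. The documents do not support that. A Fed TEAE must start at or after the fed dose, so a pre-dose event was never one. The stated food objective concerns absorption and exposure (Protocol 2.2), Part II safety is summarised descriptively by period, and SAP Section 10 plans no safety review for Part II.

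Some protection already exists. An event with a clear alternative cause can be judged not related (Protocol 10.1.3), related TEAEs are summarised separately, and both TEAEs and meal data are listed. With 8 subjects a careful reader could find such an event. None of this corrects the all-causality Fasted count or the overlap at the boundary.

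Cutting at meal start is also selective, since events on Period 2 Day -1, or on Day 1 before the meal, stay in Fasted. That is acceptable: meal start is where the fed procedure begins, and its time is recorded.

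**Conclusion.** The point holds, as a minor clarification. As written, an adverse event timed at the Period 2 dose belongs to both periods, and one that begins during the preceding breakfast is tabulated as Fasted. Neither document has a rule that resolves either case.

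The exposure is about 4 subject-hours in total, most likely involving no event or one. If one subject is affected, a Fasted incidence rises by up to 12.5 percentage points. No Fed event is lost, and no test or decision rule in the visible text depends on the Fasted-to-Fed contrast in TEAEs.

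This rests on the fixed fasted-then-fed order, which the TEAE definitions themselves use, and on a meal-to-dose interval of up to 30 minutes. Two passages need reconciling separately. Protocol 9.3 speaks of a randomly assigned treatment order, against the fixed order in SAP 3.2. Protocol 9.3 also times the dose at 30 minutes after meal start, whereas SAP 6.6 makes 30 minutes the latest time. Under either timing, the meal starts before the dose.

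**What to change.** Make both changes in SAP 9.1.9:

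1. Replace the inclusive end of the Fasted window with a strict one, so that a Fasted TEAE starts before the Period 2 dose. An onset at the dose is then Fed only.
2. Keep events with onset from the start of the Period 2 meal to before the Period 2 dose as treatment-emergent, but flag them. Show them in a separate row or column, for example *Period 2 pre-dose (after meal start)*, and leave them out of the Fasted incidence.

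Record both changes in SAP Section 11. Protocol 14.1 provides for departures from the protocol's analyses to be identified in the SAP, so no amendment under Protocol Section 17 is needed.

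The cost is a sentence or two and a programming condition on fields already held: the meal start time in the eCRF and the adverse event onset date and time. The downside is one extra row or column and a Fasted window shorter by up to about 30 minutes.

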### 4.3 Duration of Treatment

Part I: The study will be a SAD study with subjects admitting to the clinic on Day -1, and dosing on Day 1, followed by a residential period that concludes on Day 4 after assessments are completed, except in cases where the residence is extended due to safety concerns determined by the Investigator in consultation with the study Medical Monitor. An EOS visit will be performed 7 days after discharge from the in-patient unit (Day 11). The time from Screening to the EOS Visit is 39 days per cohort in Part I, inclusive of the Screening window.

Part II: The study will be a cross-over, single-dose study with 2 treatment periods. Admission will occur on Day -1, followed by dosing (Day 1), and a washout period of at least 1 week or at least 5 half-lives between dosing, whichever period is longer. The duration of the washout period could be adapted based on the review of PK data of INDV-2000. Subjects will be discharged on Day 2 unless tolerability from Part I indicates a longer stay is warranted. If that is the case, subjects will stay in the clinical unit until Day 4. If discharged on Day 2, subjects will return to the clinical unit on the morning of Day 3 and Day 4 for PK testing. Depending on PK results from Part I, the visit schedule may be modified. An EOS visit will be performed on Day 10 of the last Treatment Period (Part II, Period 2). The time from Screening to the EOS Visit is approximately 45 days, inclusive of the Screening window.

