#### 6.3 Subject Completion

A completed subject is one that has completed the EOS visit. The end of the study is defined as the last subject's last visit.

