## 10.1.1 Time Period for Collecting Adverse Events

Adverse event monitoring and reporting will begin after the subjects sign the ICF, continue throughout the study and include EOS/ET/Follow-up. Subjects will be monitored by the study site staff for untoward effects and will be released from the study after the last procedure is completed and confirmed that the subject has no residual untoward effects from the IMP that may affect safety. Treatment-emergent AEs will be defined events observed after starting administration of INDV-2000 or placebo.

Surgical procedures, planned before enrolment of the subject in the study, are not considered AEs if the condition was known before study inclusion. In this case the medical condition should be reported in the subject's medical history.

Any clinically significant symptoms will be reported as AEs. All AEs and corresponding treatment will be recorded in the eCRFs and a summary of all the safety data will be presented in the final Clinical Study Report (CSR). Any ongoing AEs will be appropriately followed up until resolution or 14 days after EOS/ET. The study site personnel will make every effort to contact the subject for a minimum of 2 attempts after which the outcome of the AE will be considered ongoing and the subject will be noted in source as lost to follow-up.

If a subject experiences the onset of an SAE within 5 days following study completion and in the opinion of the Investigator, that SAE is associated with the study drug, it will be followed and reported as described in Section 11.2.

If an SAE occurs that is deemed related to study drug, a PK sample will be taken as soon as possible after the event is reported. If possible, an additional sample should be collected when the SAE has been resolved.

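### If the Part II dosing interval is under 9 days, fed-period AEs starting in the last 1 to 2 of 9 follow-up days are not treatment-emergent and miss the primary-endpoint tables

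*SAP*

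**What the plan says.** Both documents define treatment emergence in Part II period by period. Under SAP 9.1.9, an AE belongs to Period 2 (Fed) if it starts at or after that period's dose "and within the period of time equal to the interval from Period 1 dosing to Period 2 dosing". Protocol 14.4.1 carries the same limit: "within the period of time equal to the interval from Period 1 dosing to Period 2 dosing".

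Two other definitions have no upper limit. One is the Part I definition, in those same two sections. The other is the general statement in Protocol 10.1.1: "Treatment-emergent AEs will be defined events observed after starting administration of INDV-2000 or placebo".

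The timing comes from Protocol 4.3. It requires "a washout period of at least 1 week or at least 5 half-lives between dosing, whichever period is longer" and adds: "The duration of the washout period could be adapted based on the review of PK data of INDV-2000". It also lets the visit schedule change after the Part I PK results. The Part II EOS visit is on Day 10 of Period 2, and the time from Screening to EOS is given as about 45 days. AEs are collected through EOS (Protocol 10.1.1, SAP 8.1).

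The primary endpoint in Protocol 14.4.1 is the incidence, seriousness, severity and drug relationship of TEAEs. The AE summary tables in SAP 9.1.9 are all built on TEAEs; AEs that do not qualify go to a separate listing.

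**The concern.** The fed window has the length of the dosing interval, while fed-period follow-up runs to EOS. Nothing in the plan makes the two equal. If the interval is the shorter, AEs that the study collects in the last days before EOS are not treatment-emergent by definition, whatever the investigator says about causality.

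Part II has no scheduled visit between Period 2 Day 4 and EOS (Protocol Appendix 2). EOS is therefore the only scheduled late check, with physical examination, laboratory tests, vital signs and ECG. An abnormality first found there and dated that day would fall outside the window. Protocol 10.1.2 records a change in severity as a separate event, so a late worsening would also miss the table of maximum severity.

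The same AE at the same time after dosing would count as a TEAE in Part I, and under the wording of Protocol 10.1.1, but not in the fed period.

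**Working it through.** **Inputs**
- Dosing interval I: at least 7 days, or 5 half-lives if longer (Protocol 4.3). The documents give no human half-life; Protocol 1.4 says human PK is not yet characterised.
- EOS: Period 2 Day 10, with dosing on Day 1, so 10 − 1 = 9 days after the fed dose.
- Screening window: 28 days (Protocol Appendix 2).

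**Step 1. Reproduce the stated duration.** The Period 2 dose falls on study day I + 1 and EOS on study day I + 10, so the total is 28 + I + 10 days.
- I = 7: 28 + 7 + 10 = 45, the stated figure.
- I = 8: 46. I = 9: 47.
- Check on Part I: 28 + 11 = 39, as stated.
- Counted instead as elapsed days, the total is I + 37, and 45 corresponds to I = 8.

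The stated duration therefore fits an interval of about 7 to 8 days. Because it is approximate, it does not exclude a longer one.

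**Step 2. Follow-up outside the fed window.** Days excluded = max(0, 9 − I).

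| Interval I | Window closes after fed dose | EOS after fed dose | Excluded | Share of 9 days |
|---|---|---|---|---|
| 7 days | 168 h | 216 h | 2 days | 2/9 = 22% |
| 8 days | 192 h | 216 h | 1 day | 1/9 = 11% |
| 9 days or more | 216 h or later | 216 h | 0 | 0% |

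These are shares of follow-up time, not of events.

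**Step 3. When the half-life rule would close the gap.**
- It takes the interval above 7 days only if the half-life exceeds 7 × 24 / 5 = 33.6 h.
- It takes the interval to 9 days or more only if the half-life is at least 9 × 24 / 5 = 43.2 h.

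**Step 4. How late the excluded events are.** Under the washout rule, the cut-off is at least 5 half-lives after the fed dose. With first-order decay, 2^−5 = 3.1% of the drug would remain at that point.

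**Step 5. With no cap.** Under Protocol 10.1.1, or with a window running to EOS, 0 of 9 days are excluded at any interval.

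**The case against.** The strongest reply is that the window is deliberate and prespecified. The SAP follows the statistics section of the protocol, and windows of equal length give fed and fasted conditions equal time at risk. At a 7-day interval, an uncapped fed window would set 9 days against 7. Protocol 10.1.1 can be read as a general rule separating pre-dose from post-dose events, with 14.4.1 as the specific crossover rule. Much of this stands. A reader might infer that the SAP departs from the protocol's analysis definition; it does not, and the mismatch lies within the protocol. Equal windows are defensible for comparing conditions. The documents do not state that rationale, however, and it does not justify removing late events from the overall Part II incidence.

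The reply that both ends of the calculation can move also stands. Washout and visit schedule may both change after Part I, so the gap is conditional.

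Two stronger readings are tempting but unsupported:
- A reader might infer that serious events after EOS are lost from the primary tables too, because Protocol 10.1.1 provides for them: "If a subject experiences the onset of an SAE within 5 days following study completion and in the opinion of the Investigator" judges the event associated with study drug. That provision leads to the SAE reporting in Section 11.2. The documents do not say whether such events enter the analysis database, and it is an assumption that study completion there means the subject's own EOS visit. No figure is drawn from it.
- A reader might infer that the fed/fasted comparison is biased because the Period 2 check-in falls inside a 7-day fasted window, with no counterpart in the fed window. That would argue against the equal-length window itself, which the fix keeps for that comparison. An AE reported at EOS with onset inside the window still counts, so only findings dated after the cut-off are affected.

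**Conclusion.** The point holds as a conditional and minor one. With EOS on nominal Day 10, a dosing interval of 7 days puts the last 2 of 9 fed-period days outside the TEAE window, 8 days puts 1 of 9 outside, and 9 days or more puts none. The stated duration makes 7 to 8 days plausible but not certain.

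The consequence is limited:
- At most 8 subjects are involved, and the affected AEs begin at least 5 half-lives after dosing.
- The events are not lost from the report, as a reader might infer from their absence in the tables: they are in the non-TEAE listing.
- EOS laboratory, vital-sign and ECG values are still summarised (SAP 9.1.12, 9.1.13, 9.1.15).
- An AE whose missing start date or time leaves its status undetermined still counts as treatment-emergent (SAP 9.1.9).

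SAP 9.1 describes Part II summaries by period, and the table layouts are in a separate document (SAP 12). A Part II total column may therefore exist, but one built on these definitions would omit the same events.

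Assumptions: whole-day intervals and EOS on nominal Day 10. The schedule footnotes are not in the text available, so any visit window around EOS is unknown.

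One editorial matter: the Period 1 window includes the moment of the Period 2 dose and the Period 2 window starts at it, so an AE beginning exactly then meets both definitions.

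**What to change.** - For the primary endpoint, count every Part II AE with onset at or after the first dose and through EOS or early termination as treatment-emergent, and show the result in an all-Part-II column.
- Keep the equal-length window only for the by-condition fed/fasted table. State why it is used, and footnote the number of AEs that began after it closed.
- Align Protocol 10.1.1, Protocol 14.4.1 and SAP 9.1.9, and record the change in SAP Section 11.
- Reword the Period 1 definition so that its window ends strictly before the Period 2 dose.

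The cost is wording in two documents, one table column and one footnote. The downside is that fed and fasted observation times are unequal in the uncapped count; the retained equal-length table gives the comparison over equal time.
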